#### **8.8.1 HPA-axis suppression**

The number and proportion of subjects with HPA-axis suppression at Week 4 and Week 8 will be summarised.

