Trial Design:	
This is a Phase 2, randomised, open-label, parallel-group, multicentre trial in which the investigational product, MC2-01 cream, and calcipotriene/betamethasone ointment (comparator) is investigated in subjects with clinically diagnosed extensive psoriasis vulgaris.
 
After having provided informed consent, the subjects will undergo screening procedure. Subjects that fulfil the inclusion and exclusion criteria are randomly assigned in a 1:1 ratio to receive the MC2-01 cream or the comparator.
 
Subjects assigned to the MC2-01 cream will be treated once-daily for 8 weeks and the subjects assigned to the comparator will be treated once-daily for 4 weeks.
 
At Week 4, the pharmacokinetic (PK) profile of calcipotriene (CAL), betamethasone dipropionate (BDP) and their main metabolites MC1080 and betamethasone 17-propionate, respectively, will be assessed for both treatment groups. At Week 8, the PK profile of calcipotriene, betamethasone and their main metabolites will be assessed for the MC2-01 cream treatment group only.
 
The effect of use of MC2-01 cream on the hypothalamus-pituitary-adrenal (HPA) axis and calcium metabolism will be evaluated at week 4 and week 8.
 
The maximum trial duration for each subject will be approximately 12 or 16 weeks and includes a screening period of up to 4 weeks (if washout of medication is required), a treatment period of 4 or 8 weeks, and a follow-up period of up to 4 weeks (if required for follow-up of adverse events, calcium concentrations, and/or HPA axis suppression).

Sample Size:	
It is planned to enrol approximately 60 subjects with the aim to have 25 subjects included in the PK population after 4 weeks of treatment in each treatment arm.
 
The choice of sample size in this trial is not based on statistical considerations, but rather on regulatory considerations with respect to common practice in maximum use studies evaluating pharmacokinetic profiles and evidence of HPA safety

Trial Population:	Generally healthy males or non-pregnant females, at least 18 years of age, with a clinical diagnosis of plaque psoriasis (psoriasis vulgaris) of at least 6 months duration, with a Physician Global Assessment (PGA) of disease severity of at least moderate on the trunk, limbs and/or scalp and a treatment area between 20% and 30% of the BSA, excluding psoriatic lesions on the face, genitals, and intertriginous areas.

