Statistical Methods:	
It is planned to combine the data from all centres that participate in this protocol, in order to have an adequate number of subjects for analysis. No imputation will be made for missing data.
 
Primary endpoint:
 
Systemic PK profile of the active ingredients of the MC2-01 cream and their main metabolites following once daily topical application for 4 weeks.
 
All available concentration results will be summarised using appropriate descriptive statistics for active ingredients (BDP and CAL) and for their major metabolites. Median and individual concentration versus time curves will be plotted (linear and semi-log plots).
 
Plasma PK parameters (<math>AUC_{0-t}</math>, <math>AUC_{0-\infty}</math>, <math>AUC_{0-7}</math>, <math>C_{max}</math>, and <math>T_{max}</math>, and <math>T_{1/2}</math>) will be calculated. For a given analyte, the PK parameters <math>AUC_{0-t}</math>, <math>AUC_{0-\infty}</math>, <math>T_{max}</math>, and <math>T_{1/2}</math> will be calculated if data allow. The PK parameters <math>AUC_{0-7}</math> and <math>C_{max}</math> will be calculated using standard formulas inserting the lower limit of quantification (LLoQ) in case of concentrations below the LLoQ, in which case the result is an upper limit for the PK parameter. The PK parameters will be summarised using appropriate descriptive statistics. The PK parameters <math>AUC_{0-7}</math> and <math>C_{max}</math> will be compared for the two treatment groups using analysis of variance for censored data.
 
Only for subjects assigned to the MC2-01 cream:
 
Systemic PK profile of the active ingredients of the MC2-01 cream and their main metabolites following once daily topical application for 8 weeks.
 
The PK parameters <math>AUC_{0-t}</math>, <math>AUC_{0-\infty}</math>, <math>AUC_{0-7}</math>, <math>C_{max}</math>, <math>T_{max}</math>, and <math>T_{1/2}</math> will be calculated and presented as described for Week 4.
 
Secondary endpoints for subjects assigned to the MC2-01 cream:
 
HPA axis suppression
 
The proportion of subjects with HPA-axis suppression at Week 4 and at Week 8 will be summarised using frequency counts.
 
Calcium metabolism endpoints:
 
Summary statistics will be provided for the following:
 
Observed values of and changes from Baseline (SV2) to Week 4 and Week 8 in:
 
 
• Albumin-corrected serum calcium
 

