### **8.8 Analysis of Safety**

The assessment of HPA axis suppression (using pre- and post-stimulation cortisol levels) and of changes in calcium metabolism are the primary safety endpoints in this trial.

Other assessments of safety will be based mainly on the frequency of AEs and on the number of laboratory values that fall outside of predetermined ranges, presented for the two periods, Weeks 1 to 4 and Weeks 5 to 8, separately. Adverse events will be presented in data listings and summarized by frequency and severity for each treatment group for each period. Laboratory and vital sign data will be presented in data listings. Abnormal laboratory findings will be presented. The analysis of safety will be described in the SAP.

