## 8. ANALYSIS POPULATIONS

Three analysis populations will be defined for analysis:

- Safety Population: will include all randomized subjects who have been dispensed the trial medication, excluding subjects who return all of the trial medication unopened. The Safety Population will be used for all safety analyses other than evaluation of the HPA-axis.
- HPA population: will include all subjects in the Safety population that are assigned to MC2-01 cream and who show normal HPA function at Baseline (defined as a 30-minute post-stimulation cortisol level  $\geq 18 \mu\text{g/dL}$ ). Since the objective of the analysis is to estimate the risk to subjects with normal HPA function of HPA-axis suppression following treatment, subjects who meet the definition of HPA-axis suppression at Baseline will be excluded from the analysis. The HPA population will be used for the HPA axis suppression analysis.
- Pharmacokinetic (PK) Population: will include all subjects in the Safety population who have received the planned application of treatment at the Week 4 or Week 8 visit, respectively, and have had at least one post-application blood draw for PK assessment at the corresponding visit. The PK Population will be used for the PK analysis.

---

All safety, HPA and PK analyses will be conducted according to the treatment actually received.

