## 9. DATA CONVENTIONS FOR ANALYSIS

### 9.1 General Statistical Principles

All statistical processing will be performed using the SAS system (Version 9.3 or higher).

All observed and derived variables (e.g., change from baseline) used in the summaries of analyses will be presented in by-subject listings. Descriptive statistics will be used to provide an overview of the safety and PK results. For categorical parameters, the number and percentage of subjects in each category will be presented. The denominator for percentage will be based on the number of subjects appropriate for the purpose of analysis. For continuous parameters, descriptive statistics will include number of observations, mean, standard deviation (SD), median, and range. The PK parameters will be summarised using appropriate descriptive statistics including median, lower and upper quartiles, minimum and maximum. Geometric means and coefficient of variation (CV) will be provided as appropriate.

It is planned that the data from all centers that participate in this protocol will be combined so that an adequate number of subjects will be available for analysis.

No interim analyses are planned.

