## 10.8.2 Analyses of Safety Endpoints

### 10.8.2.1 HPA-axis Suppression

The number and proportion of subjects with HPA-axis suppression at Week 4 will be summarised for the HPA population. Subjects with HPA-axis suppression at Week 4, was as described in the

protocol, contacted to discontinue use of MC2-01 cream. Subjects with HPA-axis suppression at Week 8 will be summarised overall and separately by HPA-axis suppression status at Week 4.

An additional analysis of the number and proportion of subjects with HPA-axis suppression will be summarised based on the test laboratory normal reference range established for the analytical method used by the test laboratory in the trial for the ACTH challenge test.

- In this analysis HPA suppression is defined as a 30-minute post-stimulation cortisol level  $< 14 \mu\text{g/dl}$  (test laboratory normal reference range of 14 to 36  $\mu\text{g/dl}$  for the 30-minute post-stimulation cortisol level). This analysis will be performed among MC2-01 cream subjects whose Baseline cortisol level is  $\geq 14 \mu\text{g/dl}$

All HPA-axis function test results (baseline, Week 4, Week 8, and Follow-up) will be presented in a by-subject listing for the Safety population.

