Generated on XXXXXX by XXXX / Uses: XXXX / Reference: Data Listing XXXX

Table 14.2.4.1 Summary of HPA-Axis Suppression (Based on Cosyntropin US Packing Insert)  
HPA Population

	MC2-01 Cream (N=XX)
HPA-Axis Suppression, n / N (%)	
Visit 3/ Week 4	XX/XX (XX.X)
Visit 5/ Week 8	XX/XX (XX.X)
HPA-Axis Suppressed at Week 4	XX/XX (XX.X)
HPA-Axis Not Suppressed at Week 4	XX/XX (XX.X)

Note: HPA-axis suppression is defined as a 30-minute post-stimulation cortisol level <18 µg/dL  
Generated on XX/XX/XX:XXXX by XXXXX / Uses: XXXX / Reference: Data Listings XXXX

*[Programming note: Denominator for Visit 5/Week 8 (Week 4 HPA-Axis Suppressed) row is subjects with HPA-Axis Suppressed at Week 8; denominator for Visit 5/Week 8 (Week 4 HPA-Axis Not Suppressed) row is subjects with HPA-Axis Suppressed at Week 8]*

Table 14.2.4.2 Summary of HPA-Axis Suppression (Based on Lab Reference Range)  
MC2-01 Cream Subjects with Baseline Cortisol Level  $\geq$  14  $\mu$ g/dl

MC2-01 Cream (N=XX)	
HPA-Axis Suppression, n / N (%)	
Visit 3/ Week 4	XX/XX (XX.X)
Visit 5/ Week 8	XX/XX (XX.X)
HPA-Axis Suppressed at Week 4	XX/XX (XX.X)
HPA-Axis Not Suppressed at Week 4	XX/XX (XX.X)

Note: HPA-axis suppression is defined as a 30-minute post-stimulation cortisol level  $<14 \mu$ g/dL  
Generated on XX/XX/XX:XXXX by XXXXX / Uses: XXXX / Reference: Data Listings XXXX

*[Programming note: Denominator for Visit 5/Week 8 (Week 4 HPA-Axis Suppressed) row is subjects with HPA-Axis Suppressed at Week 8; denominator for Visit 5/Week 8 (Week 4 HPA-Axis Not Suppressed) row is subjects with HPA-Axis Suppressed at Week 8]*

MC2 Therapeutics  
Protocol Number: MC2-01-C3

Page X of Y

Table 14.2.5 Summary of Calcium Metabolism  
HPA Population

MC2-01 Cream (N=XX)		
	Observed Value	Change from Baseline
Albumin-Corrected Serum Calcium (unit)		
Baseline		
N	XX	--
Mean (SD)	XX.X (XX.X)	--
Median	XX.X	--
Q1, Q3	XX, XX	--
Minimum, Maximum	XX, XX	--
Visit 3/Week 4		
N	XX	XX
Mean (SD)	XX.X (XX.X)	XX.X (XX.X)
Median	XX.X	XX.X
Q1, Q3	XX, XX	XX, XX
Minimum, Maximum	XX, XX	XX, XX
Visit 5/Week 8		
N	XX	XX
Mean (SD)	XX.X (XX.X)	XX.X (XX.X)
Median	XX.X	XX.X
Q1, Q3	XX, XX	XX, XX
Minimum, Maximum	XX, XX	XX, XX

<Continue for: 24 Hours Urinary Calcium Excretion (unit) and Ratio of Urinary Calcium to Creatinine>

MC2 Therapeutics  
Protocol Number: MC2-01-C3

Page X of Y

Table 14.2.6: Summary of Physician's Global Assessment (PGA)  
Safety Population

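### HPA-axis suppression, a primary safety endpoint meant to estimate a risk, is reported only as n/N (%); the Week 4 proportion should carry an exact 95% interval

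*Protocol*

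**What the plan says.** The protocol synopsis says: "The proportion of subjects with HPA-axis suppression at Week 4 and at Week 8 will be summarised using frequency counts". Protocol section 8.8.1 gives the same plan: "The number and proportion of subjects with HPA-axis suppression at Week 4 and Week 8 will be summarised". SAP section 10.8.2.1 repeats it: "The number and proportion of subjects with HPA-axis suppression at Week 4 will be summarised for the HPA population". It then adds a Week 8 summary, overall and split by Week 4 status, and a further analysis with suppression defined as a 30-minute cortisol below 14 µg/dL. The shells of Tables 14.2.4.1 and 14.2.4.2 carry the row label "HPA-Axis Suppression, n / N" followed by a percentage, with no interval in any row or column. The SAP's general rule in section 9.1 is no wider: "For categorical parameters, the number and percentage of subjects in each category will be presented".

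On purpose, SAP section 8 (and Protocol section 8.3 in the same terms) states that "the objective of the analysis is to estimate the risk to subjects with normal HPA function of HPA-axis suppression following treatment". Protocol section 8.8 says that HPA suppression and changes in calcium metabolism "are the primary safety endpoints in this trial".

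On numbers, the synopsis says: "It is planned to enrol approximately 60 subjects with the aim to have 25 subjects included in the PK population" after 4 weeks in each arm. Protocol section 8.2 and SAP section 6 say that the size was set by regulatory practice, including evidence of HPA safety, and not by a statistical calculation. Neither document gives a size or a precision target for the HPA population.

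**The concern.** A proportion from a few dozen subjects at most is an imprecise estimate of a risk, and the planned output does not show how imprecise. Three features of this trial make that matter more than usual.

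- Post-baseline HPA testing is done in the MC2-01 arm only (Protocol section 2.2), so no concurrent comparator rate puts the figure in context.
- The same section expects HPA effects to be infrequent with existing products. Zero or very few events is therefore a likely result, and that is where a percentage alone says least about the risk still open.
- Intervals are planned elsewhere: 90% for the PK ratio (Protocol section 8.7, SAP section 10.9.1) and 95% for the convenience scale (SAP section 10.10.3). The primary safety proportion has none.

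At stake is what the report can say it has excluded about adrenal suppression under maximal use.

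**Working it through.** The documents give no event rate, power or precision figure for this endpoint, so there is no stated number to reproduce. The check asks what an interval would show.

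**Inputs**
- Enrolment is about 60 (synopsis), allocated 1:1 (Protocol section 4.1): 60 / 2 = 30 randomised to MC2-01. This is the practical ceiling.
- The PK target is 25 per arm at Week 4 (synopsis). It is not an HPA target.
- The HPA population excludes subjects suppressed at Baseline (Protocol section 8.3, SAP section 8). A missing post-stimulation cortisol makes status missing (SAP section 10.8.1). The evaluable number can therefore fall below 25.
- Assumption: 20 to 30 evaluable subjects. The <14 µg/dL analysis has its own Baseline criterion, so its denominator may differ; its size is also unstated.

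**Formulas** (two-sided 95% Clopper-Pearson, x events in n)
- Lower limit: the 0.025 quantile of Beta(x, n − x + 1), or 0 when x = 0.
- Upper limit: the 0.975 quantile of Beta(x + 1, n − x). When x = 0 this is 1 − 0.025^(1/n).

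For zero events:
- n = 20: 1 − 0.025^(1/20) = 16.8%
- n = 25: 1 − 0.025^(1/25) = 13.7%
- n = 30: 1 − 0.025^(1/30) = 11.6%

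| Events | n = 20 | n = 25 | n = 30 |
|---|---|---|---|
| 0 | 0% (0 to 16.8) | 0% (0 to 13.7) | 0% (0 to 11.6) |
| 1 | 5.0% (0.1 to 24.9) | 4.0% (0.1 to 20.4) | 3.3% (0.1 to 17.2) |
| 2 | 10.0% (1.2 to 31.7) | 8.0% (1.0 to 26.0) | 6.7% (0.8 to 22.1) |

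With a one-sided 95% bound, 1 − 0.05^(1/n), zero events gives 13.9%, 11.3% and 9.5% for n = 20, 25 and 30.

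**How easily zero could occur.** The chance of no events is (1 − p)^n. The documents give no rate, so p is assumed.
- p = 5%: 35.8% (n = 20), 27.7% (n = 25), 21.5% (n = 30)
- p = 10%: 12.2%, 7.2%, 4.2%

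**Which rows can take an interval.** Each shell has four rows.
- Week 4: a proportion of evaluable subjects, so an interval is sound.
- Week 8 overall: subjects suppressed at Week 4 are told to stop the cream but stay in the trial and are retested at Week 8 (Protocol section 7.9.2, SAP section 10.8.2.1). The row mixes continued and stopped treatment, so an interval on it does not describe the risk under 8 weeks of use.
- Week 8 by Week 4 status (two rows): the programming note under each shell sets both denominators to subjects suppressed at Week 8. Each figure is then a share of the suppressed, not a risk. If nobody is suppressed at Week 8, it is 0/0.

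**The case against.** The best defence is that this is descriptive reporting, done consistently. Protocol section 4.2 defines the endpoint as a number of subjects, the objective is to evaluate an effect, and there is no hypothesis or decision threshold for suppression. Number and percentage is the SAP's rule for all categorical data, and the two planned intervals both belong to between-arm comparisons. The shells print n beside N and every ACTH result is listed, so any reader can derive an exact interval. The wording about estimating risk appears where the documents explain why subjects suppressed at Baseline are excluded; it is not a precision target.

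Most of this stands. There is no internal contradiction and no information is lost, which keeps the point at the level of a cheap improvement. It does not remove the point: the documents do say that the analysis estimates a risk, and the tables as designed leave the reader to work out how well.

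A reader might infer more than the documents support:
- That the sponsor would treat zero events as proof of no risk. No text says so; the misreading is only a possibility.
- That 25 to 30 subjects is the planned HPA sample. The 25 is a PK target and the HPA number is never given.
- That zero events always leaves more than 1 in 8 (12.5%) open. This holds two-sided at n = 25 (13.7%) but not at n = 30 (11.6%), nor for the one-sided bound at n = 25 (11.3%).
- That every proportion in the two tables should simply gain an interval. For the Week 8 rows as now specified, that would attach precision to the wrong quantity.

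**Conclusion.** The point holds as a low-cost improvement to the analysis, not as an error that undermines the trial. No interval is planned in either document or in the table shells for a primary safety proportion whose stated purpose is to estimate a risk. Assuming 20 to 30 evaluable MC2-01 subjects, zero events at Week 4 leaves a true risk of up to 16.8% to 11.6% compatible with the data at the two-sided 95% exact level. One or two events widen that to upper limits between 17.2% and 31.7%. The upper limits depend on the evaluable number, which the documents do not give, and would be higher if it fell below 20. The conclusion applies directly to Week 4; the Week 8 rows need other corrections first.

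**What to change.** 1. In SAP section 10.8.2.1 and Tables 14.2.4.1 and 14.2.4.2, add a two-sided 95% Clopper-Pearson interval to the Week 4 suppression proportion, for both the <18 and the <14 µg/dL analyses. Refer to its upper limit when stating what risk has been excluded.
2. Add an interval to the overall Week 8 proportion only with a label saying that the row includes subjects told to stop the cream after Week 4 suppression.
3. Add intervals to the Week 8 rows by Week 4 status only after the programming notes are changed, so that each denominator is the subjects in that Week 4 status group with a Week 8 result.

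The Week 4 change can be made at once, with a short SAP statement and one table column. The Week 8 changes also need a label and an edited programming note in each shell. No new data, subjects or procedures are required. The downside is an extra column and a result that looks less precise.

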#### **8.8.2 Calcium metabolism endpoints**

Summary statistics will be provided for the following:

Observed values of and changes from Baseline to Week 4 and Week 8 in:

- Albumin-corrected serum calcium
- 24 hours urinary calcium excretion
- Ratio of urinary calcium to creatinine

#### **8.8.3 Adverse events**

Adverse events will be coded using Medical Dictionary for Regulatory Activities (MedDRA) terminology. Treatment-emergent adverse events will be summarized by the overall incidence of at least one event, incidence by body system, and incidence by body system and preferred term. Each subject will contribute only once (e.g., the first occurrence) to each of the rates, regardless of the number of occurrences (events) the subject experiences. Treatment-emergent AEs will be summarised by severity (mild, moderate, or severe), and by relationship to trial product (none, unlikely, possible, probable, or definite). An adverse event is treatment-emergent if its date of onset is Day 1 (Baseline) or later.

Discontinuations from the trial due to AEs and SAEs will be listed by subject.

#### **8.8.4 Other safety variables**

Clinical laboratory values will be reported as complete listings of individual subject data.

Clinical laboratory data will be summarized by presenting shift tables using extended normal ranges (baseline to most extreme post-baseline value), by presenting summary statistics of raw data and change from baseline values (means, medians, SDs, ranges), and by the flagging of notable values in data listings.

Data from other tests (e.g., vital signs, ECG results) will be considered as appropriate and listed. Notable values will be flagged, and any other information collected will be listed as appropriate. Any statistical tests performed to explore the data will be used only to highlight any interesting comparisons that may warrant further consideration.

Vital signs will be summarised at each visit, both as absolute values and as change from Baseline, with descriptive statistics.

### **8.9 Analysis of Other Endpoints**

#### **8.9.1 Physician global assessment**

Investigator ratings of disease severity will be summarised by trial visit using frequency counts for each treatment. The proportion of subjects with treatment success, defined as a minimum 2-point decrease from Baseline in the physician's global assessment (PGA) on the trunk, limbs, and scalp will be summarized.

#### **8.9.2 Psoriasis treatment convenience scale**

Subject assessment of treatment convenience at Week 4 using a Psoriasis Treatment Convenience Scale will be summarized and further compared between MC2-01 cream and the active comparator using mixed effect model with treatment as a systematic effect and study site as a random effect.

### **8.10 Quality of Life Analysis (Not Applicable)**

Not applicable.

## **9.0 CHANGES IN THE PLANNED TRIAL**

### **9.1 Protocol Amendments**

Except for administrative changes, any changes or additions to this clinical trial protocol require a written protocol amendment that must be approved by the IRB before implementation.

These requirements for approval should in no way prevent any immediate action from being taken by the investigator or MC2 in the interests of preserving the safety of all subjects included in the trial. If an immediate change to the protocol is felt to be necessary by the investigator and is

implemented for safety reasons, MC2 or designee should be notified and the IRB should be informed according to their reporting requirements.

